### 8.3.5 Pregnancy

- Pregnancies in female participants and female partners of male participants will be reported after the start of study intervention until the follow-up visit.
- If a pregnancy is reported, the Investigator should inform the Sponsor within 24 hours of learning of the pregnancy and should follow the procedures outlined in Appendix 4 ([Section 10.4](#)).
- Abnormal pregnancy outcomes (eg, spontaneous abortion, fetal death, stillbirth, congenital anomalies, ectopic pregnancy) are considered SAEs.

### 8.3.6 Guidelines for reporting product complaints

Any defect in the IMP/NIMP must be reported as soon as possible by the Investigator to the monitoring team that will complete a product complaint form within required timelines.

Appropriate information (eg, samples, labels or documents like pictures or photocopies) related to product identification and to the potential deficiencies may need to be gathered. The Investigator will assess whether or not the quality issue has to be reported together with an AE or SAE.

## 8.4 TREATMENT OF OVERDOSE

The Sponsor does not recommend specific treatment for an overdose.

In the event of an overdose, it is recommended that the Investigator take the following actions:

1. Contact the Medical Monitor, if deemed necessary.
2. Closely monitor the participant for any hypoglycemia, AEs/SAEs and laboratory abnormalities, as appropriate.
3. Document appropriately in the eCRF (see [Section 8.3](#)).

Decisions regarding dose interruptions or modifications will be made by the Investigator based on the clinical evaluation of the participant.

## 8.5 PHARMACOKINETICS

- Whole blood samples will be collected for measurement of plasma concentrations of insulin aspart as specified in the PK flow chart (see [Section 1.3](#)). Instructions for the collection and handling of biological samples will be provided by the Sponsor or designee. The actual date and time (24-hour clock time) of each sample must be recorded.
- Samples will be used to evaluate the PK of SAR341402/insulin aspart. Each plasma sample will be divided into 2 aliquots (1 each for PK and a back-up). Samples collected for analyses of SAR341402/insulin aspart plasma concentration may also be used to evaluate safety or efficacy aspects related to concerns arising during or after the study.

## **8.6 PHARMACODYNAMICS**

Pharmacodynamic parameters are not evaluated in this study.

## **8.7 GENETICS**

Genetics are not evaluated in this study.

## **8.8 BIOMARKERS**

### **8.8.1 Immunogenicity assessments**

Antibodies to insulin aspart, including neutralizing antibodies, will be evaluated in plasma samples collected from all participants according to the SoA ([Section 1.3](#)). Additionally, plasma samples should also be collected at the final visit from participants who discontinued study intervention. Participants need to come to the site fasting without having injected any meal-time insulin (SAR341402 or NovoLog) for at least 8 hours. Blood samples for antibody measurements will be collected before any insulin is administered and in a fasting state. All samples will be tested by a central laboratory blinded to intervention allocation.

Plasma samples will be screened for antibodies binding to insulin aspart and the titer and cross-reactivity to human insulin of confirmed positive samples will be reported. Other analyses including assessment of neutralizing capacity of confirmed positive samples may be performed to further characterize the immunogenicity of insulin aspart.

The detection and characterization of antibodies to insulin aspart will be performed using a validated assay method by or under the supervision of the Sponsor. Antibodies may be further characterized and/or evaluated for their ability to neutralize the activity of the study intervention(s). Further analyses of immune responses to insulin aspart may be conducted up to two years after the last sample collection.

## **8.9 HEALTH ECONOMICS**

Health Economics and Health Economics parameters are not evaluated in this study.

## 9 STATISTICAL CONSIDERATIONS

### 9.1 STATISTICAL HYPOTHESES

The primary analysis will be performed based on natural log-transformed  $AUC_{last}$ , AUC, and  $C_{max}$ . The 90% CI for the ratio of geometric means for  $AUC_{last}$ , AUC, and  $C_{max}$  between the two treatment arms (SAR341402/NovoLog switching arm and NovoLog non-switching arm) should be within 80-125%, corresponding to the following composite null and alternative hypotheses tested at an alpha level of 0.05:

- H0: The ratio of geometric means for  $AUC_{last}$ , AUC, or  $C_{max}$  between SAR341402/NovoLog switching arm and NovoLog non-switching arm is outside the pre-defined acceptance range 80-125%.
- H1: The ratio of geometric means for  $AUC_{last}$ , AUC, and  $C_{max}$  between SAR341402/NovoLog switching arm and NovoLog non-switching arm is within the pre-defined acceptance range 80-125%.

### 9.2 SAMPLE SIZE DETERMINATION

Approximately 184 participants will be randomly assigned to either one of the treatment groups, alternating use of SAR341402 and NovoLog or continuous use of NovoLog (in a 1:1 ratio), with a minimum of 146 evaluable participants (73 per treatment group) for the primary PK evaluation expected at the end of the study. If the number of study participants with evaluable PK data is determined to have been reached before all planned 184 participants are randomized, then the study randomization may be stopped sooner.

The sample size calculations are performed based on the expected variability of the primary PK endpoints  $AUC_{last}$ , AUC, and  $C_{max}$  following injection of a predefined, fixed dose of SAR341402 or NovoLog (0.15 U/kg) at Week 16.

A sample size of 146 evaluable participants (73 participants per arm) will ensure that the 90% CI for the estimated treatment ratio is within the acceptance range of [0.8 – 1.25] with at least 90% power; assuming a true ratio between 0.95 and 1.05 (switching arm / non-switching arm) and a total standard deviation on natural log scale of 0.35 or lower.

Sample size calculations were made using SAS® Software Version 9.4.

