### **Number of participants:**

Approximately 184 participants will be randomly assigned to either one of the treatment groups, alternating use of SAR341402 and NovoLog or continuous use of NovoLog (in a 1:1 ratio), with a minimum of 146 evaluable participants (73 per treatment group) for the primary PK evaluation expected at the end of the study. If 146 study participants with evaluable PK data can be determined to have been reached before all planned 184 participants are randomized, then the study randomization may be stopped sooner.

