### 3.1 APPROPRIATENESS OF MEASUREMENTS

The primary endpoints will be  $AUC_{last}$ ,  $AUC$ , and  $C_{max}$  following injection of a single dose of 0.15 U/kg SAR341402 (in the switching arm) or NovoLog (in the non-switching arm) at Week 16. As the rapid-acting insulins SAR341402 and NovoLog are used flexibly as prandial insulin at meal-times, no dosing intervals can be defined. Consequently, the primary endpoints will be  $C_{max}$ ,  $AUC_{last}$ , and  $AUC$  and not  $AUC_{tau}$  as proposed in the FDA Guidance for Interchangeability (1). Blood samples for these PK measurements will be taken for an 8-hour period, taking into account the PK profile of SAR341402 observed in the previous Phase 1 study PDY12695. In this study, a median  $T_{max}$  of approximately 1.2 hour and a mean half-life of approximately 1.2 hours were observed for SAR341402. Thus, an 8-hour sampling period is deemed appropriate to sufficiently cover (90% of AUC according to FDA guidance) individual PK profiles.

HbA1c is an index of average glucose over the preceding weeks-to-months. It is a "weighted" average of blood glucose levels during the preceding 120 days, as glucose levels in the 30 days prior to the measurement contribute substantially more to the level of HbA1c than do glucose levels 90-120 days earlier (9). HbA1c is also the most widely accepted measure of overall, long-term blood glucose control in patients with diabetes (4, 10).

HbA1c will be determined in a central laboratory blinded to study treatment. The assessment of HbA1c and insulin dose changes will support the assessment of the clinical relevance of treatment emergent AIAs and any outliers identified in the PK analysis. As the study is not powered for efficacy evaluations, the data obtained will be considered of supportive value only to the (primary) PK and (secondary) immunogenicity data obtained.

Immunogenicity analyses will include the determination of the AIA status, AIA titers, anti-insulin aspart neutralizing antibodies, and cross-reactivity with human insulin. The potential impact of AIAs on safety, particularly as related to hypersensitivity reactions and local injection site reactions will be evaluated. Anti-insulin aspart antibodies may change the PK and PD of the insulin by binding the insulin, resulting in an overall unstable glycemic control. Therefore, the potential effect of AIAs on glycemic control (HbA1c), insulin dose and hypoglycemia will also be assessed.

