#### **2.4.4 Analyses of pharmacokinetic endpoints**

##### **2.4.4.1 Analyses of primary pharmacokinetic endpoints**

###### ***Primary analysis***

The primary analysis will be performed on the PK population, based on natural log-transformed  $AUC_{last}$ ,  $AUC$ , and  $C_{max}$ . The 90% CI for the ratio of geometric means for  $AUC_{last}$ ,  $AUC$ , and  $C_{max}$  between the two treatment arms (switching arm versus non-switching arm) should be within 80-125%, corresponding to the following composite null and alternative hypotheses tested at an alpha level of 0.05:

- $H_0$ : The ratio of geometric means for  $AUC_{last}$ ,  $AUC$ , or  $C_{max}$  between the switching arm and the non-switching arm is outside the predefined acceptance range 80-125%
- $H_1$ : The ratio of geometric means for  $AUC_{last}$ ,  $AUC$ , and  $C_{max}$  between the switching arm and the non-switching arm is within the predefined acceptance range 80-125%

For primary analysis, the natural log-transformed  $AUC_{last}$ ,  $AUC$ , and  $C_{max}$  will be statistically analyzed using an analysis of variance, including the fixed categorical effects of treatment arm (switching arm, non-switching arm) and randomization stratum (screening HbA1c <8.0%,  $\geq 8.0\%$ ).

Estimate and 90% CI for the ratio of geometric means between the two arms (switching arm / non-switching arm) will be computed separately for  $AUC_{last}$ ,  $AUC$ , and  $C_{max}$ , from the linear model framework using re-transformation. The 90% CIs for the ratio of geometric means of  $AUC_{last}$ ,  $AUC$ , and  $C_{max}$  should be within 80-125%.

Additionally, PK parameters will be summarized by treatment using descriptive statistics (for details, see [Section 2.5.7](#)).

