#### ***2.4.4.3 Multiplicity issues***

The type of analysis for multiple primary PK endpoints cannot inflate the type 1 error risk above 0.05. No adjustment of alpha/confidence level will be performed.

Further PK endpoints will be analyzed purely descriptively.

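### The stated power of at least 90% is for one PK parameter; the primary criterion needs all three, and joint power falls below 90% at the limits of the stated assumptions.

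*Protocol*

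**What the plan says.** Protocol 9.2, repeated in SAP 1.3, gives one power statement for 73 evaluable participants in each arm: "with at least 90% power; assuming a true ratio between 0.95 and 1.05 (switching arm / non-switching arm"). The variability behind this figure is taken as "a total standard deviation on natural log scale of 0.35 or lower". What is powered is a single event, namely that "the 90% CI for the estimated treatment ratio is within the acceptance range of" 0.8 to 1.25. The treatment ratio is in the singular, and neither section says whether the power is per parameter or joint.

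The success rule is joint. Protocol 9.1 sets out "composite null and alternative hypotheses tested at an alpha level of 0.05": the null holds if the ratio for any one of AUClast, AUC or Cmax is outside 80-125%, and the alternative requires all three to be inside. SAP 2.4.4.1 repeats this; the 90% CI "should be within 80-125%, corresponding to the following composite null and alternative hypotheses tested at an alpha level of 0.05". SAP 2.4.4.3 adds "The type of analysis for multiple primary PK endpoints cannot inflate the type 1 error risk above 0.05", which concerns false positives only.

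The number of evaluable participants may be held at the minimum. The protocol synopsis says "If 146 study participants with evaluable PK data can be determined to have been reached before all planned 184 participants are randomized", randomization may stop early.

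**The concern.** When every one of several endpoints must pass, no alpha adjustment is needed, but there is a cost in power. The probability that all three pass is at most the probability for the weakest one, and usually lower. The plan deals with the first half of this and is silent on the second.

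The power statement is a guarantee over a stated range, and it follows directly after the composite hypotheses in the protocol. It is natural to read it as the chance that the trial meets its primary criterion anywhere in that range. If it is really per-parameter power, the sponsor's risk of missing the criterion at the edges of the range is understated. The option to stop at 146 evaluable participants would also be exercised on a power figure that does not describe the criterion.

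**Working it through.** **Inputs from the documents.** Limits 0.80 and 1.25; 90% CI, so each one-sided test is at 0.05; n = 73 per arm; log SD σ = 0.35; true ratio θ from 0.95 to 1.05; ANOVA with arm and one two-level stratum, so df = 2 × 73 − 3 = 143.

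**Input the documents do not give.** The correlations among log AUClast, log AUC and log Cmax. Assumed: 0.95-0.99 between the two AUCs and 0.5-0.9 between each AUC and Cmax. Wider ranges are shown for sensitivity.

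**Step 1: reproduce the stated figure for one parameter.** SE = σ√(2/n) = 0.35 × √(2/73) = 0.0579. The distance to the nearer limit is ln(0.95/0.80) = 0.1719 at θ = 0.95 and ln(1.25/1.05) = 0.1744 at θ = 1.05. By normal approximation, power is Φ(0.1719/0.0579 − 1.645) = 90.7% at 0.95 and 91.4% at 1.05. The exact two one-sided tests calculation, using t critical values and integrating over the sample variance, gives at SD 0.35:

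| n per arm | θ = 0.95 | θ = 1.05 |
|---|---|---|
| 71 | 89.6% | 90.3% |
| 72 | 89.98% | 90.7% |
| 73 | 90.34% | 91.0% |
| 74 | 90.69% | 91.4% |

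So 73 is the smallest n per arm that reaches 90% for one parameter at 0.95, with about 0.3 points to spare. At θ = 1.00 the single-parameter power is 97.1%.

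**Step 2: bounds on joint power that need no assumed correlation value.** Joint power cannot exceed single-parameter power, so the ceiling is 90.3% at 0.95 and 91.0% at 1.05. With independent parameters it is 0.9034³ = 73.7% and 0.9103³ = 75.4%. With every correlation at 0.999 it is still only 89.9% at 0.95 (90.6% at 1.05).

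**Step 3: joint power under the assumed correlations.** Simulation of three correlated log mean differences with Wishart-distributed variances, 400,000 replicates. Success means all three 90% CIs lie within the limits. 73 per arm, SD 0.35 and the same ratio for all three:

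| AUClast-AUC corr. | AUC-Cmax corr. | θ = 0.95 | θ = 1.05 |
|---|---|---|---|
| 0.95 | 0.5 | 82.1% | 83.2% |
| 0.95 | 0.7 | 83.6% | 84.7% |
| 0.95 | 0.9 | 86.0% | 86.9% |
| 0.99 | 0.5 | 83.0% | 84.1% |
| 0.99 | 0.7 | 84.5% | 85.5% |
| 0.99 | 0.9 | 86.7% | 87.6% |

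The chance of missing the criterion is therefore between 100 − 87.6 = 12.4% and 100 − 82.1 = 17.9%.

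**Step 4: where the shortfall ends.** Same correlations and SD 0.35:

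- Ratio 0.96: 86-90%; ratio 1.04: 87-91%.
- Ratio 0.97 or 1.03: 90-93%.
- Ratio 1.00: 94-96%.

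At ratio 0.95 with smaller SDs:

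- AUC SDs of 0.30 and Cmax at 0.35: 87-90%.
- All three at 0.32, AUC-AUC correlation 0.99: about 90-92%.

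**Step 5: sample size.** Joint 90% at ratio 0.95 and SD 0.35 (AUC-AUC correlation 0.99) needs about 89, 86 or 82 evaluable per arm for an AUC-Cmax correlation of 0.5, 0.7 or 0.9. If all 184 randomized participants were evaluable (92 per arm, an upper bound), joint power at 0.95 would be about 91-93%.

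**The case against.** The strongest reply is that the plan contains no miscalculation. The sample-size text refers to one treatment ratio, SAP 2.4.4.1 computes the intervals separately, and read per parameter the figure is exactly right. That stands as far as it goes: what is missing is the words saying so. But neither document says them, and the only success criterion defined is the joint one.

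Second, the size of the gap depends on correlations and on a worst corner, with all three parameters at SD 0.35 and at the same edge ratio. This is also fair. The SD is given as an upper bound, and at lower SDs or ratios near 1 the joint figure is 90% or close to it. The two AUCs should also be almost the same quantity: Protocol 3.1 reports a half-life of about 1.2 hours against 8 hours of sampling, so the 74% for independent parameters is only a mathematical floor. With an AUC-AUC correlation of 0.99 the range at 0.95 is 83-87%. The direction does not depend on any of this, because the ceiling at 0.95 is 90.3%. The edge ratio and the SD limit are the plan's own.

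Third, this is the sponsor's risk and cannot produce a false claim of similarity. That is correct, and it is why the remedy is a matter of wording. The 146 is a minimum, but early stopping means a larger number cannot be relied on.

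**Conclusion.** The concern holds. The figure of at least 90% is the power for a single parameter and does not describe the plan's own success rule at the limits of the range it claims.

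With SD 0.35 and a common ratio of exactly 0.95 or 1.05 for all three parameters, joint power is about 82-88% under the assumed correlations. It reaches 90% at those ratios only if the parameters are almost perfectly correlated: above about 0.999 at 0.95 and about 0.995 at 1.05. Across the assumed correlations, joint power is about 90% or better for ratios of roughly 0.97 to 1.03; at the strongest of them, 90% is also reached at 0.96 and 1.04.

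The single-parameter result and the ceiling follow from the documents alone. The 82-88% rests on correlations that the documents do not supply. The calculation also takes all 73 per arm as evaluable for every parameter. SAP 2.5.7.1 drops AUC values extrapolated by more than 20%, which could lower n for AUC; that was not modelled.

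**What to change.** In Protocol 9.2 and SAP 1.3, state that the power of at least 90% is for each of AUClast, AUC and Cmax separately. Then add one sentence with the joint power and the ratio, SDs and correlations behind it. For example: *With SD 0.35 for all three parameters, a true ratio of exactly 0.95 or 1.05, and assumed correlations of 0.95-0.99 between the AUCs and 0.5-0.9 with Cmax, joint power is about 82-88%; at a ratio of 1.00 it is about 94-96%.*

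Alternatively, state the conditions under which joint power reaches 90%: SD about 0.32 at ratio 0.95 with an AUC-Cmax correlation of about 0.7, or ratios of about 0.97 to 1.03 with SD 0.35.

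The assumed SDs and correlations should be replaced by estimates from the sponsor's Phase 1 study PDY12695 if its data are suitable. Protocol 3.1 already relies on that study for the sampling period ("taking into account the PK profile of SAR341402 observed in the previous Phase 1 study PDY12695"). Beside the early-stop sentence, note that stopping at 146 evaluable participants carries this joint power.

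The cost is two or three sentences. N, the analysis model, the data collected and type I error do not change. The stated power becomes less favourable at the edges of the range.

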### 9.3 POPULATIONS FOR ANALYSES

For purposes of analysis, the following populations are defined (Table 4):

**Table 4 - Populations for analyses**

Population	Description
Screened	All participants who sign the ICF
Randomized	All screened participants who have a treatment kit number allocated and recorded in the IRT database, regardless of whether the treatment kit was used
Evaluable for PK (PK)	All participants without deviation that could significantly impact the PK analysis (eg, missing or incorrect SC injection on PK profile day) and for whom PK data are considered sufficient and interpretable
Intent to Treat (ITT)	All randomized participants, irrespective of compliance with the study protocol and procedures, analyzed in the treatment group to which they are randomized
Per Protocol (PP)	Subset of the ITT population, which includes all randomized and exposed participants, who do not definitively discontinue IMP allocated by randomization during the 16-week period, who perform Week 16 visit and who do not present major or critical protocol deviations that could significantly impact the analysis
Safety	All randomized participants who receive at least one dose of IMP (regardless of the amount of IMP administered). Participants will be analyzed according to the intervention they actually received.
Immunogenicity (AIA)	All participants from the safety population with at least one AIA sample available for analysis (ie, collected during the on-treatment period and at least 8 hours after the last administration of meal-time insulin). Participants will be analyzed according to the intervention they actually received.

AIA: anti insulin aspart antibody; ICF: informed consent form; IMP: investigational medicinal product; IRT: interactive response technology; ITT: intent to treat; PK: pharmacokinetic; PP: per protocol; SC: subcutaneous

### 9.4 STATISTICAL ANALYSES

A statistical analysis plan (SAP) will be developed and finalized before database lock and will describe the participant populations to be included in the analyses, and procedures for accounting for missing, unused, and spurious data. This section is a summary of the planned statistical analyses of the primary and secondary endpoints and any changes to the planned analyses will be addressed in the SAP.

### 9.4.1 Pharmacokinetic analyses

**Table 5 - Pharmacokinetic analyses**

Endpoint	Statistical Analysis Methods
Primary: AUC last , AUC, C max following injection of a predefined, fixed dose of SAR341402 or NovoLog (0.15 U/kg) at Week 16	
Primary PK analysis will be based on the PK population. For participants with insufficient data for some but not all PK parameters, the evaluable PK parameters will be included in the analysis.
 
PK parameters will be summarized by treatment using descriptive statistics.
 
The impact of switching between SAR341402 and NovoLog on AUClast, AUC, and Cmax will be assessed. For primary analysis, the natural log-transformed AUClast, AUC, and Cmax will be statistically analyzed using an analysis of variance, including the fixed categorical effects of treatment arm (SAR341402/NovoLog switching arm, NovoLog non-switching arm) and randomization strata. Estimate and 90% CI for the ratio of geometric means between the two arms (SAR341402 from switching arm / NovoLog from non-switching arm) will be computed for AUClast, AUC, and Cmax, from the linear model framework using re-transformation. The 90% CI for the ratio of geometric means of AUClast, AUC, and Cmax should be within 80-125%.

Secondary: Time to C max (T max ) following injection of a predefined, fixed dose of SAR341402 or NovoLog (0.15 U/kg) at Week 16	T max will be summarized by treatment in the PK population using descriptive statistics.

AUC: area under the concentration curve; Cmax: maximum concentration; PK: pharmacokinetic; Tmax: time to maximum concentration

